##### D. Privacy Protections

All patients are protected by HIPPA, FERPA and medical information is maintained in a secure EMR. d

#### 4.2 Obtaining Identifiable Information About Non-Subjects NA

#### 4.3 Number of Subjects

##### A. Total Number of Subjects

A review completed by RUBIs determined that 26 subjects is needed to make formal determination of validity.

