#### A. Research Procedures

The project will be a randomized control trial where all patients who present to our office with groin based hip pain, radiographic evidence of FAI, and a positive anterior impingement test would be recruited. Two groups will then be separated: one being the traditional physical therapy group, and the other with the addition of BFR to traditional PT.

Standard radiographs would be obtained and would include a standard AP pelvis, Dunn view, and false profile view.

Initial office visit would record the patient's degree of hip flexion, result with anterior impingement testing, alpha angle (on dunn view), lateral center edge angle (on AP pelvis) and anterior center edge angle (on false profile view). Additionally, we would evaluate for the presence of ischial spine sign, cross over sign, and if the proximal femoral physis was present on radiographs. MRI will not be routinely ordered on the initial visit, but if this has already been obtained, the presence of a labral tear based on the radiology report will be recorded.

Demographic data would be collected which would include age, sex, primary sport, duration of symptoms, and previous treatment.

Physical therapy protocol would include traditional PT focusing on core and gluteal strengthening. Additionally, avoidance of activities and exercises that result in pain or high hip flexion and internal rotation would be recommended. After 6 weeks, if the patient remained symptomatic, an ultrasound guided intra-articular hip injection would be offered to the patient. If the patient remained persistently symptomatic, then hip arthroscopy would be offered to the patient.

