**D. Endpoints**

- Patient ops out of study
- Re-injury/Alternate injury
- Completion of 8 week rehab program

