**1.5 Sample Size Justification**

Previous similar studies have recruited 35 to 60 subjects for similar studies looking at functional outcomes with BFR treatment. We are conducting an a priori power analysis with Rutgers RUBIES to determine the sample size required for 80% power with an alpha of 5%.

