## 6.0 Data Management Plan

### 6.1 Data Analysis

Rutgers RUBIES will conduct a priori power analysis for determining the appropriate sample size. Functional outcome measures (ROM, strength, muscle endurance) will be analyzed via Student's t test. PROMs (IHOT, mHHS, VAS, PROMIS-10) will be analyzed via Wilcoxon unranked sum test.

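### Section 4.3 A gives 26 as both the number needed and the total, with no stated loss allowance; read naturally, enrolment misses the 80% power target once more than one or two patients lack week-8 data

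*Protocol*

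**What the plan says.** - **Target (Protocol 1.5).** "We are conducting an a priori power analysis with Rutgers RUBIES to determine the sample size required for 80% power", with alpha at 5%. No effect size, SD, sidedness or loss rate is given here or elsewhere in the protocol.
- **Number (Protocol 4.3 A, Total Number of Subjects).** The section reports, as the result of a completed review by the same statistics group, that "26 subjects is needed to make formal determination of validity". No other enrolment figure appears. The sentence does not say whether 26 counts enrolled or evaluable patients, and it does not restate the power.
- **Design (Protocol 1.3 A).** "Two groups will then be separated: one being the traditional physical therapy group, and the other with the addition of BFR to traditional PT". The allocation ratio is not stated.
- **Ways of leaving (Protocol 1.3 D, 4.4 A).** Section 1.3 D lists "Patient ops out of study" and re-injury or another injury beside completion of the 8-week programme. Section 4.4 A lets patients drop out whenever they wish. No expected frequency, replacement rule or inflation is given.
- **Commitment (Protocol 1.3 C).** Two visits a week for 8 weeks, which is 16 visits.
- **Analysis (Protocol 6.1).** A t test for ROM, strength and endurance, and a Wilcoxon test for the patient-reported measures. The same section still says that "Rutgers RUBIES will conduct a priori power analysis for determining the appropriate sample size".

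**The concern.** The number described as needed is also the number to be recruited. If 26 is what the 80% target requires in the analysis, the design leaves no room for the exits that the protocol itself provides for. The t and rank tests named in 6.1 use only patients who have a value, so a patient without week-8 data is lost to the week-8 comparison unless some other provision is made.

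With about 13 patients per arm, each loss counts. A null result could be read as coming from a trial with 80% power when the number analysed supported less. The direction of this point does not depend on the effect size. Only its size does.

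**Working it through.** **Inputs from the protocol.** Total 26 (4.3 A); target power 80% and alpha 5% (1.5); two groups (1.3 A); Student's t test for strength (6.1).

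**Inputs assumed.** 1:1 allocation; two-sided two-sample test; 26 as the smallest even total that reaches 80%; losses split evenly between arms. The protocol states none of these.

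**1. Can 26 be reproduced?** No. Without an effect size and SD it can be neither confirmed nor refuted. It can only be inverted to find the standardised differences d for which it would be the right answer.

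**2. Formula.** With n per arm, power = P(|T| > t(0.975; 2n − 2)), where T is noncentral t with 2n − 2 degrees of freedom and noncentrality d × √(n/2).

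**3. Range of d consistent with 26.**
- n = 13 gives 80% at d = 1.1454 (noncentrality 1.1454 × √6.5 = 2.920, 24 df).
- n = 12 gives 80% at d = 1.1968 (noncentrality 1.1968 × √6 = 2.932, 22 df).
- So 26 is the smallest even total that reaches 80% for d from about 1.145 to just under 1.197.

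**4. Power with fewer evaluable patients, d held fixed.**

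| Evaluable | Loss out of 26 | Power at d = 1.1454 | Power at d = 1.1968 |
|---|---|---|---|
| 26 | 0 | 80.0% | above 80% |
| 24 | 2 (7.7%) | 76.5% | 80.0% |
| 22 | 4 (15.4%) | 72.4% | 76.1% |
| 20 | 6 (23.1%) | 67.8% | 71.6% |

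At the lower d, a single loss (25 evaluable) gives 78.2%. At the upper d, the rounding up to 26 absorbs two losses. The shortfall is therefore clear only beyond one or two.

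**5. Sensitivity to sidedness.** With a one-sided 5% test, n = 13 gives 80% at d = 1.004. At that d, 24, 22 and 20 evaluable give 77.0%, 73.5% and 69.7%. The pattern is the same.

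**6. How likely is full retention?** The protocol gives no loss rate. As an illustration, if each patient independently had a 10% chance of loss, all 26 would be retained with probability 0.9^26 = 0.065, about 6%.

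**The case against.** The strongest reply is that the premise is inferred. Section 4.3 A does not say that 26 is a count of completers. An already inflated total could properly stand under that heading, and the underlying calculation is not shown. Nor does the section mention power; the 80% comes from 1.5. Both observations are correct, and they make the conclusion conditional. But the wording of 4.3 A is that of a requirement, nothing suggests an allowance, and 1.5 names the same group's calculation as the source of the sample size. If 26 does include an allowance, the protocol still needs to say so and give the evaluable number.

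A second reply is that leaving the programme need not mean missing data, and that the handling of missing values may be left to a statistical analysis plan that is not at hand. That stands as to analysis. It does not settle what the enrolment total, which the protocol itself fixes, is meant to deliver. Similarly, the number needed could be a minimum, and no text says that recruitment stops at 26. But no text says that it continues either.

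A reader might infer several stronger things that the documents do not support:

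- **The 80% holds only if nobody leaves.** This is true only in the literal sense and only if 26 is exact. One loss costs about 2 points, and rounding may absorb one or two.
- **The protocol expects opt-outs and injuries.** It provides for them and gives no frequency.
- **26 is miscalculated.** No stated figure is shown to be wrong.
- **The pending wording in 1.5 and 6.1 means the calculation was not done.** Section 4.3 A says that it was completed. The other sentences look like leftover text, which is a clerical conflict and no evidence about attrition.

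**Conclusion.** The point holds in conditional form. On the natural reading, 26 is the analysable number for 80% power, it is also the whole stated enrolment, and no allowance covers the exits that the protocol provides for. The planned enrolment then falls short of its own target once more than one or two patients lack week-8 data. The shortfall is about 0-4 points with 24 evaluable, 4-8 with 22 and 8-12 with 20.

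These sizes rest on 1:1 allocation, a two-sided t test, 26 as the smallest even total giving 80%, and loss rates that are assumptions. The effect size behind them is back-solved, so none of the percentages should be read as the trial's actual power. An allowance already inside the 26 cannot be excluded. In that case what remains is that the protocol does not say so.

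**What to change.** 1. In 4.3 A, state that 26 is the number of patients with week-8 data. If it already includes an allowance, state the smaller evaluable number instead.
2. In the same paragraph, give the expected loss and the power that an enrolment of 26 delivers at that loss. Use the effect size and SD from the completed calculation and state both. The percentages above come from a back-solved effect size and should not be copied into the protocol.
3. In 1.5 and 6.1, replace the sentences that describe the calculation as pending with this same figure.

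The cost is one protocol paragraph and two replaced sentences. The downside is that the stated power becomes slightly less favourable.

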##### B. Total Number of Subjects If Multicenter Study NA

##### C. Feasibility

Given there have been other studies published in the literature that also evaluated BFR with similar enrollement, this study is feasible to be carried out over one year. With several physicians managing patients with FAI, there is significant volume to draw the necessary patients.

#### 4.4 Consent Procedures

**A. Consent Process**

▪ **Location of Consent Process**

All potential participants will be appraised of the study by participating surgeon during the office visit to assess their reported hip pain. Subjects will sign a formal Consent to participate in the study in the physical therapy clinic where they will undergo their therapy. (Somerset, Wall, Morganville and Avenel)

**Ongoing Consent**

NA

▪ **Individual Roles for Researchers Involved in Consent**

Individual surgeons will identify patients who may qualify for involvement in the study. Physical therapists will collect acknowledgement and consent to participate in the study..

▪ **Consent Discussion Duration**

Patients will be provided the study description to review for 5 minutes. The physiotherapist will answer any questions the patient may have about involvement in the study. The patient may drop out of the study at any time without reprisal.

▪ **Coercion or Undue Influence**

Patients will be advised of the study, provided information about the study, and then the therapist will leave the room, allowing the patient to review in private. Patients are also given the opportunity to ask questions prior to making a decision about participation. .

▪ **Subject Understanding**

Patients will be asked to explain their role in the study prior to the physical therapist, prior to signing of the acknowledgement.

▪ **Protecting Privacy**

Patients will be provided a private room to review study description and materials.

**B. Waiver or Alteration of Consent Process**

▪ **Waiver or Alteration Details**

NA

▪ **Destruction of Identifiers**

▪ **Use of Deception/Concealment**

NA

**Minimal Risk Justification**

a. **Alternatives**

b. **Subject Debriefing**

**C. Documentation of Consent**

▪ **Documenting Consent**

Participants will be asked to sign study consent prior to enrolling in the study. Participants can opt out of the study at any time without reprisal.

▪ **Waiver of Documentation of Consent (i.e., will not obtain subject's signature) NA**

**4.5 Special Consent Populations**

NA

**A. Enrolling Minors-Subjects Who Are Not Yet Adults NA**

▪ **Parental Permission**

▪ **Non-Parental Permission**

▪ **Assent Process**

▪ **Documentation of Assent**

▪ **Reaching Age of Majority During Study**

**B. Enrolling Wards of the State**

NA.

- Research Outside of NJ Involving Minors

**C. Enrolling Non-English-Speaking Subjects**

NA

- Process for Non-English-Speaking Subjects
- Short Form Consent for Non-English Speakers

**D. Enrolling Adults Lacking Decision-Making Capacity (Surrogate Consent)**

NA

- Assessing Adult Capacity to Consent
- Selecting a Surrogate & Consent Process
- Subject Assent
- Selecting a Witness to the Surrogate Consent Process NA
- Removing a Subject -

The subject will provide written intention of withdrawal to the PI. The PI will notify study coordinator and supervising therapist of subject withdrawal.

**E. Special Consent Considerations**

NA

**4.6 Economic Burden and/or Compensation for Subjects**

**A. Expenses**

There are no expenses related to this participating in the study that will be incurred by the study participant. .

**B. Compensation/Incentives**

Participation in the study is voluntary and study participants will not receive any compensation.

**C Compensation Documentation NA**

**4.7 Risks of Harm/Potential for Benefits to Subjects**

**A. Description of Risks of Harm to Subjects**

- Reasonably Foreseeable Risks of Harm

There is no more than minimal risk to participate in this study. Use of BFR may cause some leg soreness, bruising, short term numbness or tingling. The study also requires a time commitment to be able to participate in physical therapy twice a week.

- Risk of Harm from an Intervention on a Subject with an Existing Condition NA
- Other Foreseeable Risks of Harm

Other foreseeable risks may include risks associated with a possible loss of confidentiality.

- Observation and Sensitive Information

**B.**

**C. Procedures which Risk Harm to Embryo, Fetus, and/or Pregnant Subjects**

NA.

**D. Risks of Harm to Non-Subjects**

NA

**E. Assessment of Social Behavior Considerations**

NA

**F. Minimizing Risks of Harm**

All therapy-related activities will be performed by trained medical professionals with years of training. All collected data will be recorded directly to REDCap by study members at the time of the research visit. Access to REDCap will be password-protected and limited to only study team members, and data recording will be performed on password-protected computers at UOA sites.

All supervising therapists have received formal training with the use of BFR and will utilize the pressure cuff appropriately. Subjects will be evaluated after each use and appropriate care provided if there are any associated injuries.

- **Certificate of Confidentiality NA**
- **Provisions to Protect the Privacy Interests of Subjects**

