**B. Data Points**

- Objective strength measurements utilizing a hand held dynamometer
- Results of PROM.
- Demographic and surgical data

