**2.0 Project Management**

Project management will be overseen by the supervisor of physical therapy, PI and study coordinator. Each will be involved in regular review of therapy, adherence to study guidelines and reporting of any adverse incidents.

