###### ▪ Exclusion Criteria

- History of DVT, VTE, or clotting disorder
- History of CRPS or current radicular leg pain
- Trochanteric bursitis as primary diagnosis
- Pre-existing hip condition (SCFE, perthes, AVN)
- Osteoarthritis (Tonnis >2) on xrays
- Stress fracture

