**A. Data/Safety Monitoring Plan**

Input of data will be periodically monitored by the study coordinator to ensure complete data collection within RedCap.

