**B. Data/Safety Monitoring Board Details**

In the event of a significant issue, the PI, Study coordinator, and supervisor of Physical Therapy will discuss and appropriately resolve the issue. Any significant issues will be reported directly to the IRB.

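### The only scheduled harm check follows cuff use, none is stated for the traditional PT arm's sessions, and adverse events are not a listed data item, so comparable harm counts by arm could not be reported

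*Protocol*

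**What the plan says.** Section 4.7 A of the protocol names the expected harms: "Use of BFR may cause some leg soreness, bruising, short term numbness or tingling." It places the overall risk no higher than minimal. Section 4.7 F then gives the check: "Subjects will be evaluated after each use and appropriate care provided if there are any associated injuries." The sentence before it is about therapists' training with the pressure cuff, so the check is tied to the cuff.

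The data points in section 1.3 B run from "Objective strength measurements utilizing a hand held dynamometer" through patient-reported measures to "Demographic and surgical data". The outcomes in 1.6 B, the instruments in 1.9 A and the schedule in 1.10 cover strength, endurance, range of motion, the pain VAS and questionnaires. None lists an adverse event item.

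Four other places touch on harm:
- Section 2.0 gives the therapy supervisor, the investigator and the coordinator a regular review that includes "adherence to study guidelines and reporting of any adverse incidents".
- Section 1.3 D lists re-injury or a different injury among the endpoints.
- Section 6.3 is marked not applicable, but its part A reads: "Input of data will be periodically monitored by the study coordinator to ensure complete data collection within RedCap."
- Section 6.3 B has the team resolve a significant issue and adds: "Any significant issues will be reported directly to the IRB."

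**The concern.** A harm check that follows one arm's intervention looks harder for harm in that arm. Any soreness, numbness or injury in a patient on traditional PT has to be volunteered or noticed. The same event in a BFR patient meets a scheduled evaluation. A difference in counts would then mix a true effect with a difference in how closely patients were examined.

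The timing also fits the protocol's own list of harms poorly. Whether numbness or tingling was short-lived cannot be known straight after the session in which it began. The exclusion criteria in 4.1 C include "History of DVT, VTE, or clotting disorder", yet no section plans to ask about related symptoms at later visits.

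At stake is a modest but useful product of the trial: a descriptive harm count in each arm, collected the same way. Section 1.2 hopes to influence rehabilitation recommendations, and 4.7 A asserts minimal risk. Both call for such a count.

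**Working it through.** The point rests on reading sections together. The arithmetic only shows what complete capture could deliver.

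**Is harm sought equally in both arms?**
- Traditional PT runs twice a week for 8 weeks, and so does the BFR protocol (1.6 A): 2 × 8 = 16 sessions per patient.
- BFR arm: one evaluation after each cuffed session, so 16 per patient. With 13 patients and full attendance, 13 × 16 = 208 evaluations.
- Traditional PT arm: no evaluation is stated for any of the 16 sessions. The endurance test in 1.6 B is done with and without occlusion. If controls take it, the after-use check reaches them at those assessments, but not at their therapy sessions.

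**Is there a stated place to record harm?** All collected data go straight to REDCap and no paper copies are kept (4.7 F, 6.2). Sections 1.3 B, 1.6 B, 1.9 A and 1.10 name no harm item. The monitoring in 6.3 A checks completeness of the data entered, so it would not notice the absence of an item that was never listed.

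**Do the other passages fill the gap?** Section 2.0 sets a duty to report but gives no question, time point, definition or form. The injury entry in 1.3 D stands beside opting out and completing the programme, so it reads as a way participation ends; it would not cover bruising or numbness. Section 6.3 B starts only once an issue is judged significant, a term it does not define.

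**What could full capture show?** Inputs: 26 subjects in total (4.3 A), taken as given; the allocation ratio is not stated, so 1:1 is assumed, giving 26 / 2 = 13 on BFR.
- Upper 95% limit on the event rate after 0 events in n patients, one-sided: 1 − 0.05^(1/n). For n = 13 this is 0.206.
- Two-sided (Clopper-Pearson): 1 − 0.025^(1/n). For n = 13 this is 0.247.
- Range for the allocation assumption: no split of 26 could do better than n = 26 on BFR, which gives 0.109 and 0.132.
- Chance of at least one event among 13, 1 − (1 − p)^13: 12% at a true rate of 1%, 23% at 2%, 49% at 5% and 75% at 10%.
- Fisher's exact test, 13 against 13, with no control events: 4 BFR events give p = 0.096 and 5 give p = 0.039. At least 5 would be needed for two-sided p < 0.05.

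**The case against.** The best defence is that the protocol has other routes for harm. The reporting duty in 2.0 is not limited by arm, cuff use or timing. The injury endpoint applies to everyone. Every patient meets a therapist twice a week, and the VAS is taken at weeks 2, 4 and 8. The objective in 1.1 A is effectiveness, and 26 patients could not settle safety whatever was recorded.

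Much of this stands, and it rules out several stronger readings that a reader might infer:
- *That delayed harms are missed.* Not supported. They can surface at the next visit and be reported under 2.0. What holds is that no section fixes a question to find them, and nothing is stated after week 8.
- *That control sessions have no harm check, or that the after-use result is not recorded.* The protocol is silent on both, and silence is not proof of absence.
- *That 2.0 and 6.3 B contradict each other.* They can be read as two tiers: the team reports any incident, and significant ones go to the IRB. They are unreconciled, with the threshold undefined, but not in plain conflict.
- *That the exclusion list shows the cuff is expected to cause clots.* The list gives no reasons and applies to both arms.

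The defence does not remove the imbalance. Frequent visits make asking easy, but no passage says anyone asks, and a general duty to report will yield more where patients are examined by schedule. Nor can this be left to a statistical analysis plan: a plan can say how harms are tabulated, but it cannot recover what was not collected.

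**Conclusion.** The point holds in a limited form. The one scheduled harm check is tied to cuff use, no equivalent is stated for the traditional PT arm's sessions, and adverse events are not a listed data item. Followed as written, the plan gives unstructured and unequal ascertainment, so harm counts could not be compared between arms or used to support the minimal-risk statement.

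A reader might go further and conclude that this flaw is why the trial cannot say whether BFR is safe. The documents do not support that. Safety is not an objective, and the limit of about 21% (one-sided) or 25% (two-sided) after 0 of 13 events reflects the sample size, not the missing harm item. It also assumes 1:1 allocation and complete data on all 13. What is lost is the ability to report even that descriptive bound on an equal footing. The effectiveness comparison is not affected.

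**What to change.** Keep the after-use evaluation and the commitment to care in 4.7 F, and add to them:
- List adverse events among the data points in 1.3 B.
- Record them on one short REDCap item, identical in both arms, at each therapy visit. It asks about symptoms since the last visit, using the harms named in 4.7 A plus any injury or other event. Repeat it at the week-8 assessment.
- Report descriptive counts by arm, without a claim of safety, and state that systematic collection ends at the week-8 assessment.
- Reconcile 2.0, 4.7 F and 6.3 (the not-applicable entry and part B) so that it is clear every incident is recorded and which ones go to the IRB.

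How a positive answer affects further cuff use is for the sponsor to decide and state.

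The cost is a protocol amendment, one REDCap item and slightly more data entry by the therapist already present.
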